### ***Treatment Discontinuation***

Subjects will continue study treatment until the documentation of confirmed PD, intolerable toxicity, death, withdrawal of active participation/consent in the study, or loss to follow-up, or as long as they benefit from therapy according to the opinion of the responsible study investigator and discussed with the sponsor.

Subjects are not permitted to start any other anti-myeloma therapy before progression is confirmed or subject cannot tolerate study treatment. A treatment discontinuation visit will be required for all subjects who discontinue treatment.

- If POM is permanently discontinued, then the subject must be permanently discontinued from all study treatments.
- For Patients in Cohort B and Cohort C, if DARA is withheld or permanently discontinued, then POM, and LD-Dex dosing may be continued.
- If LD-dex dosing is withheld or permanently discontinued, then POM and DARA (for patients in Cohort B and Cohort C) dosing may be continued.

See dose administration guidance in Section 8.3.

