### ***Laboratory Assessments for Safety Parameters***

With the exception of pregnancy tests, all laboratory assessments for safety parameters will be performed and reviewed by the central laboratory; however, tests that may result in dose interruption and/or modification should also be performed locally to allow for treatment related decisions during subject visits. Results from local laboratories will not be collected, unless specifically requested by the sponsor in which case they may be entered into an unscheduled visit on the eCRF. At Study Day 1 subject must meet eligibility criteria based on local or central lab results prior to initiating study therapy.

If screening visit results are  $\leq 7$  days prior to enrollment, these laboratory assessments are not required to be repeated at Cycle 1 Day 1.

- **Hematology Laboratory Tests.** Hematology includes: white blood cell (WBC) count with differential, absolute neutrophil count (ANC), absolute lymphocyte count

(ALC), hemoglobin, hematocrit, platelet count, and mean corpuscular volume. Hematology will be performed at screening, on Day 1 of each cycle, and at treatment discontinuation.

- **Serum Chemistry Laboratory Tests.** Serum chemistry includes: calcium (corrected), albumin, total bilirubin, alkaline phosphatase, aspartate aminotransferase (AST)/serum glutamic oxaloacetic transaminase (SGOT), alanine aminotransferase (ALT)/serum glutamic pyruvic transaminase (SGPT), gamma glutamyl transferase (GGT), sodium, potassium, blood urea nitrogen, creatinine, and lactate dehydrogenase. Serum chemistry labs will be performed at screening, on Day 1 ( $\pm$  3 days) of every cycle, and at treatment discontinuation. If PD is noted based on corrected serum calcium level, a repeat serum chemistry test should be performed as soon as possible to confirm PD.
- **Infectious Tests.** Human immunodeficiency virus (HIV), Hepatitis A, Hepatitis B and Hepatitis C. Infectious testing will be performed at screening for Cohort C only.
- **Urinalysis.** Urinalysis includes: specific gravity, pH, glucose, bilirubin, protein, ketones, blood and microscopic analysis (casts, bacteria, red blood cells [RBCs], and WBCs). Urinalysis will be performed at screening, and at treatment discontinuation.
- **Estimation of Renal Function.** The assessment will be performed using the Cockcroft-Gault estimate of creatinine clearance (CrCl).

*Cockcroft-Gault Formula* ([Cockcroft, 1976](#); [Luke, 1990](#))

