### **Efficacy Assessments**

Disease progression status will be assessed by the Investigator at each treatment cycle and at treatment discontinuation. Tumor response including progressive disease will be assessed according to the IMWG uniform response criteria ([Durie, 2006](#)) and modified to add criteria for MR ([Kyle, 2009](#)). All treatment decisions will be made by the treating physician based on response as assessed using the mIMWG criteria (per [Appendix B](#)).

Daratumumab is a human IgG kappa monoclonal antibody that can be detected on both, the serum protein electrophoresis (SPEP) and immunofixation (IFE) assays used for the clinical

monitoring of endogenous M-protein. This can lead to false positive SPEP and IFE assay results for subjects with IgG kappa myeloma protein impacting initial assessment of complete responses by International Myeloma Working Group (IMWG) criteria. In subjects with persistent very good partial response, consider other methods to evaluate the depth of response.

Survival status will be collected for all subjects during the long-term follow-up phase.

All efficacy laboratory assessments will be performed and reviewed by the central laboratory. These efficacy assessments include laboratory tests used as part of standard care: Serum beta-2 microglobulin (at screening only), myeloma paraprotein protein electrophoresis and immunofixation, serum immunoglobulins, and serum free light chain assay.

Efficacy assessments are to be performed at the start of each new cycle. If a new cycle is delayed more than 7 days (but less than 28 days) from the protocol-defined 28-day dosing cycle, an unscheduled visit should be performed for efficacy assessments prior to initiation of the next cycle. If the delay is greater than 28 days, these efficacy assessments should be performed every 28 days ( $\pm 3$  days) until a new cycle can begin. For subsequent cycles following a delayed cycle, efficacy assessments should be performed at the start of each new cycle.

The efficacy assessments will be documented in the source documents and recorded on the eCRF.

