### 7.3. Exclusion Criteria

The presence of any of the following will exclude a subject from study enrollment:

1. Any of the following laboratory abnormalities:
  - Absolute neutrophil count < 1,000/ $\mu$ L
  - Platelet count < 75,000/ $\mu$ L for subjects in whom < 50% of bone marrow nucleated cells are plasma cells; or a platelet count < 30,000/ $\mu$ L for subjects in whom  $\geq$  50% of bone marrow nucleated cells are plasma cells.
  - Severe renal impairment (Creatinine Clearance [CrCl] < 30 mL/min) requiring dialysis.
  - Corrected serum calcium > 11.5 mg/dL (> 2.8 mmol/L)
  - Hemoglobin < 8 g/dL (< 4.9 mmol/L; prior red blood cell transfusion or recombinant human erythropoietin use is permitted)
  - Serum SGOT/AST or SGPT/ALT > 3.0 x the upper limit of normal (ULN)
  - Serum total bilirubin > 2.0 mg/dL (34.2  $\mu$ mol/L); or > 3.0 x ULN for subjects with hereditary benign hyperbilirubinemia
2. Prior history of malignancies, other than MM, unless the subject has been free of the disease for more than 5 years. Allowed exceptions include the following:
  - Basal or squamous cell carcinoma of the skin

- Carcinoma in situ of the cervix or breast
  - Incidental histological finding of prostate cancer (TNM [tumor, nodes, metastasis] stage of T1a or T1b)
3. Previous therapy with pomalidomide or daratumumab
  4. Hypersensitivity to thalidomide, LEN, or dex (this includes  $\geq$  Grade 3 rash during prior thalidomide or LEN therapy)
  5. Subjects who received an allogeneic bone marrow or allogeneic peripheral blood stem cell transplant less than 12 months prior to initiation of study treatment and who have not discontinued immunosuppressive treatment for at least 4 weeks prior to initiation of study treatment and are currently dependent on such treatment.
  6. Subjects with any one of the following:
    - Congestive heart failure (NY Heart Association Class III or IV)
    - Myocardial infarction within 12 months prior to starting study treatment
    - Unstable or poorly controlled angina pectoris, including Prinzmetal's variant angina pectoris
  7. Subjects who received any of the following within 14 days of initiation of study treatment:
    - Major surgery (kyphoplasty is not considered major surgery)
    - Use of any anti-myeloma drug therapy
  8. Use of any investigational agents including for the treatment of multiple myeloma within 28 days or 5 half-lives (whichever is longer) of treatment, unless approved by the sponsor.

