## Appendix B: International Myeloma Working Group Response Criteria (Continued)

**Table 11: International Myeloma Working Group Relapse Criteria**

Relapse Category a	Relapse Criteria
Progressive Disease	
Requires only one of the following:
 
Increase of <math>\geq 25\%</math> from nadir in:
 
Serum M-component and/or (the absolute increase must be <math>\geq 0.5</math> g/dL)b
 
Urine M-component and/or (the absolute increase must be <math>\geq 200</math> mg/24 hours)
 
In subjects without measurable serum and urine M-protein levels the difference between involved and uninvolved FLC levels, the absolute increase must be <math>> 100</math> mg/dL.
 
Bone marrow plasma cell percentage, the absolute % must be <math>\geq 10\%</math>c
 
Definite development of new bone lesions or soft tissue plasmacytomas increase in the size of existing bone lesions or soft tissue plasmacytomas.
 
Development of hypercalcemia (corrected serum calcium <math>> 11.5</math> mg/dL or 2.65 mmol/l) that can be attributed solely to the plasma cell proliferative disorder.

Clinical Relapse (Not used for TTP or PFS)	
Clinical relapseb requires one or more of:
 
Development of new soft tissue plasmacytoma or bone lesions
 
Definite increase in the size of existing plasmacytomas or bone lesions. A definite increase is defined as a 50% (and at least 1 cm) increase as measured serially by the sum of the products of the cross-diameters of the measurable lesion
 
Hypercalcemia (<math>> 11.5</math> mg/dL [2.65 mmol/l])
 
Decrease in hemoglobin of <math>\geq 2</math> g/dL (1.25 mmol/l)
 
Rise in serum creatinine by 2 mg/dL or more (177 <math>\mu</math>mol/l or more)

Relapse from CRd	
Any one or more of the following:
 
Reappearance of serum or urine M-protein by immunofixation or electrophoresis
 
Development of <math>\geq 5\%</math> plasma cells in the bone marrowc
 
Appearance of any other sign or progression (ie, new plasmacytoma, lytic bone lesion, or hypercalcaemia)

a All relapse categories require 2 consecutive assessments made at any time before classification as relapse or disease progression and/or the institution of any new therapy.

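### The Table 11 calcium threshold for progressive disease pairs 11.5 mg/dL with 2.65 mmol/L, which are different values, and the protocol does not say which governs

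*Combined protocol and SAP*

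**What the plan says.** The Progressive Disease row of Table 11 (Appendix B) needs only one of its listed criteria to be met. One of them is newly developed hypercalcemia, with corrected serum calcium > 11.5 "mg/dL or 2.65 mmol/l) that can be attributed solely to the plasma cell proliferative disorder". The Clinical Relapse row repeats the pair as > 11.5 "mg/dL [2.65 mmol/l"; that row is marked as not used for TTP or PFS. Footnote a adds a confirmation rule: "All relapse categories require 2 consecutive assessments made at any time before classification as relapse or disease progression".

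Section 6 treats calcium as a working PD trigger: "If PD is noted based on corrected serum calcium level, a repeat serum chemistry test should be performed". It gives no threshold or unit there. Under Efficacy Assessments it says: "All treatment decisions will be made by the treating physician based on response as assessed using the mIMWG criteria". The Protocol Summary, under Treatment Discontinuation, says: "Subjects will continue study treatment until the documentation of confirmed PD", and the same sentence goes on to allow treatment for as long as the investigator sees benefit. Section 10.6 defines PFS and TTP from investigator-determined PD, and duration of response from the first confirmed PD.

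The only other cut-off for corrected calcium is in exclusion criterion 1, Section 7.3: "Corrected serum calcium > 11.5 mg/dL (> 2.8 mmol/L".

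**The concern.** A threshold given in two units should be one threshold. Here the two figures look like an ordinary conversion but differ by more than rounding can explain. Calcium alone can establish PD, so the choice of figure decides whether some subjects have progressed.

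At stake are the event dates for PFS, TTP and duration of response, and a reason to consider stopping treatment. Only the Progressive Disease row can move PFS and TTP dates. Any effect on the primary endpoint, ORR, would be indirect and slight.

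**Working it through.** **Inputs.** The Table 11 pair is 11.5 mg/dL and 2.65 mmol/L. The molar mass of calcium, 40.078 g/mol, is a physical constant that the documents do not give; values from 40 to 40.08 were also tried.

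**Formula.** mmol/L = (mg/dL × 10) / molar mass, and the inverse.

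**Attempt to reproduce the printed pair.**
- 11.5 × 10 / 40.078 = 2.869 mmol/L (2.869 to 2.875 over the molar masses tried). The table prints 2.65.
- 2.65 × 40.078 / 10 = 10.62 mg/dL (10.60 to 10.62). The table prints 11.5.
- For the pair to agree, the molar mass would have to be 115 / 2.65 = 43.4 g/mol. Rounding cannot produce that.

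**Width of the band where the figures disagree.**
- In SI units: 2.869 − 2.65 = 0.219 mmol/L.
- In mg/dL: 11.5 − 10.62 = 0.88 mg/dL, and 0.88 / 11.5 is about 7.6% of the mg/dL threshold.

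**Control check on other unit pairs**, using standard conversion constants:

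| Item | Place | Converted | Printed |
|---|---|---|---|
| Hemoglobin 2 g/dL | Table 11 | 20 / 16.114 = 1.24 mmol/L | 1.25 |
| Creatinine 2 mg/dL | Table 11 | 2 × 88.4 = 176.8 µmol/L | 177 |
| Bilirubin 2.0 mg/dL | Section 7.3 | 2 × 17.1 = 34.2 µmol/L | 34.2 |
| Hemoglobin 8 g/dL | Section 7.3 | 80 / 16.114 = 4.96 mmol/L | 4.9 |
| Calcium 11.5 mg/dL | Section 7.3 | 2.87 mmol/L | 2.8 |
| Calcium 11.5 mg/dL | Table 11 | 2.87 mmol/L | 2.65 |

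The other two pairs in Table 11 agree closely. The Section 7.3 calcium pair is slightly off: 2.8 × 40.078 / 10 = 11.2 mg/dL. The Table 11 calcium pair is clearly wrong.

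**Search for a governing rule.** The Table 11 footnotes do not rank the two figures. The serum chemistry paragraph of Section 6 orders a repeat test without naming a value. The endpoint definitions in Section 10.6 refer back to the criteria. Exclusion criterion 1 concerns entry, but it uses 11.5 mg/dL, and its SI figure conflicts with 2.65.

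**The case against.** The strongest answer is that the mismatch will rarely matter. A subject must develop a calcium value inside a band 0.22 mmol/L wide, have it confirmed, have it attributed solely to myeloma, and meet no other PD criterion. Section 6 sends safety chemistry to a central laboratory and generally does not collect local results, so mixed units across sites are less likely. The affected endpoints are secondary and descriptive. All of this stands and limits the size of the point. It does not settle which figure governs, because the reporting unit is not stated and investigators determine PD.

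A reader might go further in three ways that the documents do not support:

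- **That a calcium-only PD call forces treatment to stop.** The Protocol Summary and Section 4.1 let treatment continue while the investigator judges that the subject benefits (discussed with or approved by the sponsor), and Section 12 lists PD only as a sufficient reason for discontinuing.
- **That subjects could enter the study already progressed.** A subject at 2.70 mmol/L (10.8 mg/dL) would pass both printed entry figures while above 2.65. But the PD row requires hypercalcemia to develop, and no rule says that entry and PD limits must match. The overlap merely suggests that 11.5 mg/dL was intended.
- **That the 2.8 mmol/L in exclusion criterion 1 can be classified with confidence.** It may be 2.87 cut to one decimal, as the nearby "Hemoglobin < 8 g/dL (< 4.9 mmol/L; prior red blood cell transfusion" appears to be for 4.96. Ordinary rounding would give 2.9. The documents do not say, so it is neither a proven second error nor proven harmless.

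The protocol presents these criteria as published IMWG criteria, modified to add minor response. Whether the pair was carried over from that source or mistyped cannot be told from the documents. Either way, an investigator has two numbers and no rule.

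**Conclusion.** The inconsistency is real and lies in an operative definition. Between 2.65 and 2.87 mmol/L (10.6 to 11.5 mg/dL), the same confirmed, myeloma-attributed, newly developed corrected calcium, with no other PD criterion met, is PD by one printed figure and not by the other. It can change PFS, TTP and duration-of-response dates and can contribute to a decision to stop treatment.

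The severity is minor. The number of affected subjects cannot be computed from the documents; that it is small is an assumption. That anyone would apply the mmol/L figure is also an assumption, since the reporting unit is not given. Section 10.6 plans Kaplan-Meier medians and confidence intervals for these endpoints and no test, so no formal conclusion depends on the choice. The documents point to 11.5 mg/dL as the intended value through exclusion criterion 1, but that is inference.

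**What to change.** Have the clinical team confirm the intended threshold, checking the cited criteria. Assuming it is 11.5 mg/dL, write > 11.5 mg/dL (> 2.87 mmol/L) in both the Progressive Disease and Clinical Relapse rows of Table 11. Print the same SI value in exclusion criterion 1, so that 11.5 mg/dL does not carry two SI equivalents in one protocol.

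Cohorts A and B are already fully enrolled (56 + 112 = 168 subjects), so also check whether any PD date recorded there rests on calcium alone with a value inside the band.

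The cost is three corrected figures at the next amendment and a short data check. Under Section 14.5 the amendment needs IRB/EC approval unless it is classed as administrative. No new assessments are required, and the planned analyses do not change.

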## **Appendix C: Skeletal (Bone) Survey Films**

The following are the minimum plain radiological films required for the skeletal (bone) survey:

- Lateral skull
- AP and lateral cervical spine
- AP and lateral thoracic spine
- AP and lateral lumbar spine
- PA chest
- AP pelvis
- AP upper extremities, shoulder to elbow
- AP lower extremities, hip to knee

Other radiological films may be necessary to view symptomatic areas or known pre-existing lesions in skeletal regions not included in the films above.

## **Appendix D: Pomalidomide Pregnancy Risk Minimization Plan for Celgene Clinical Trials**

The Pomalidomide Pregnancy Risk Minimization Plan is a standalone document.

## Appendix E: ECOG Performance Status Scale

**Table 12: ECOG Performance Status Scale**

Score	Description
0	Fully active, able to carry on all pre-disease performance without restriction
1	Restricted in physically strenuous activity but ambulatory and able to carry out work of a light or sedentary nature, eg, light housework, office work.
2	Ambulatory and capable of all self-care but unable to carry out any work activities. Up and about more than 50% of waking hours.
3	Capable of only limited self-care, confined to bed or chair more than 50% of waking hours.
4	Completely disabled. Cannot carry on any self-care. Totally confined to bed or chair
5	Dead

## Appendix F: Estimation of Renal Function

The primary assessment for renal function will be performed using the by Cockcroft-Gault formula for estimation of creatinine clearance (CrCl):  $\text{CrCl (mL/min)} = (140 - \text{age}) (\text{weight [kg]}) / 72 (\text{serum creatinine [mg/dL]})$ ; for females, the formula is multiplied by 0.85 ([Cockcroft, 1976](#); [Luke, 1990](#)).

Creatinine clearance also need be determined based on a 24-hour urine collection at Screening visit; for all other visits, a 24-hour urine collection may also be used as the primary assessment for renal function at the investigator's discretion.

## **Appendix G: QT Drugs by Risk Group**

To access a current list of QT-prolonging drugs grouped by risk of torsades, possible risk of torsades, and conditional risk of torsades visit <http://www.qtdrugs.org/>.

[figure not shown]
## Appendix H: Staging Systems for Multiple Myeloma

**Table 13: Staging Systems for Multiple Myeloma**

Stage	Durie-Salmon Criteria	ISS Criteria
I	All of the following: Hemoglobin value > 10 g/dL Serum calcium value normal or < 12 mg/dL Bone x-ray, normal bone structure (scale 0), or solitary bone plasmacytoma only Low M-component production rates IgG value < 5 mg/dL; IgA value < 3 mg/dL Urine light chain M-component on electrophoresis < 4 g/24 h	Serum beta-2 microglobulin < 3.5 mg/L Serum albumin ≥ 3.5 g/dL
II	Neither Stage I nor Stage III	Neither Stage I nor Stage III
III	One or more of the following: Hemoglobin value < 8.5 g/dL Serum calcium value normal or > 12 mg/dL Advanced lytic bone lesions (scale 3) High M-component production rates IgG value > 7 mg/dL; IgA value > 5 mg/dL Urine light chain M-component on electrophoresis > 12 g/24 h	Serum beta-2 microglobulin ≥ 5.5 mg/L
Subclassification Criteria A Normal renal function (serum creatinine value < 2.0 mg/dL) B Abnormal renal function (serum creatinine value ≥ 2.0 mg/dL)		Not applicable

Source: [Durie, 1975](#); [Greipp, 2005](#).

## Appendix I: EQ-5D

## Appendix J: List of Abbreviations

**Table 14: List of Abbreviations**

Abbreviation	Definition
AE	Adverse Event
ALC	Absolute Lymphocyte Count
ALT	Alanine Aminotransferase
ANC	Absolute Neutrophil Count
ASCO	American Society of Clinical Oncologists
ASCT	Autologous Stem-cell Transplantation
AST	Aspartate Aminotransferase
BTZ	Bortezomib
CR	Complete Response
CrCl	Creatinine Clearance
CT	Computed Tomography
DARA	Daratumumab
dex	Dexamethasone
DLT	Dose-limiting Toxicity
DoR	Duration of Response
DTT	Dithiothreitol
DVT	Deep Vein Thrombosis
EC	Ethics Committee
ECG	Electrocardiogram
ECOG	Eastern Cooperative Oncology Group
eCRF	Electronic Case Report Form
EE	Efficacy Evaluable
EMP	Extramedullary Plasmacytoma
EU	European Union
FCBP	Female of Child Bearing Potential
FDA	Food and Drug Administration
FISH	Fluorescence In Situ Hybridization
FLC	Free Light-Chain
GCP	Good Clinical Practice
GCSF	Granulocyte Colony-Stimulating Factor

## Appendix J: List of Abbreviations (Continued)

**Table 14: List of Abbreviations (Continued)**

Abbreviation	Definition
GGT	Gamma Glutamyl Transferase
HDAC	Histone deacetylase
HiDex	High-dose Dexamethasone
HIV	Human Immunodeficiency Virus
IAT	Indirect Antiglobulin Test (also known as indirect Coombs test)
IB	Investigator's Brochure
IC 50	Half Maximal Inhibitory Concentration
ICD	Informed Consent Document
ICH	International Conference on Harmonisation
IFE	Immunofixation
IFM	Intergroupe Francais du Myelome
IMiDs	Immunomodulating drugs
IMWG	International Myeloma Working Group
IP	Investigational Product
IRB	Institutional Review Board
IRR	Infusion Related Reaction
ITT	Intent-to-treat
IVRS/IWRS	Interactive Voice Response System/Web Response System
LD-dex	Low-dose Dexamethasone
LEN	Lenalidomide
LPS	Lipopolysaccharide
MedDRA	Medical Dictionary for Regulatory Activities
mIMWG	Modified International Myeloma Working Group
MM	Multiple Myeloma
MR	Minor Response
MRD	Minimal Residual Disease
MRI	Magnetic Resonance Imaging
MTD	Maximum Tolerated Dose
NCCN	National Comprehensive Cancer Network
NCI-CTCAE	National Cancer Institute Common Terminology Criteria for Adverse Events

## Appendix J: List of Abbreviations (Continued)

**Table 14: List of Abbreviations (Continued)**

Abbreviation	Definition
ORR	Overall Response Rate
OS	Overall Survival
PD	Progressive Disease
PE	Pulmonary Embolism
PFS	Progression-Free Survival
PI	Proteasome Inhibitors
POM	Pomalidomide
PR	Partial Response
QoL	Quality of Life
QTc	QT Corrected
RBC	Red Blood Cell
SAE	Serious Adverse Event
SD	Stable Disease
SGOT	Serum Glutamic Oxaloacetic Transaminase
SGPT	Serum Glutamic Pyruvic Transaminase
SPEP	Serum Protein Electrophoresis
SPM	Second Primary Malignancy
SUSAR	Suspected Unexpected Serious Adverse Reaction
TEAE	Treatment-Emergent Adverse Event
TNM	Tumor, Nodes, Metastasis
TNF	Tumor Necrosis Factor
TTP	Time to Progression
TTR	Time to Response
ULN	Upper Limit of Normal
UPEP	Urine Protein Electrophoresis
US	United States
VGPR	Very Good Partial Response
VTE	Venous Thromboembolism
WBC	White Blood Cell

